6.5.3 Sensitivity Analyses

The primary analyses for all none time event outcomes (i.e continuous, binary and count outcomes) will consider any missing data to be missing at random (MAR) and complete case analysis carried out. However, if comparison of patterns of missingness and descriptive differences between treatment arms indicate this assumption is not valid, additional sensitivity analyses may be carried out and methods of imputation will be included in detail in the statistical analysis plan.

To ensure the reliability of the analysis of key secondary outcome measures, we will conduct a sensitivity analysis under various scenarios. This will involve evaluating the secondary outcomes; number of readmissions, number of exacerbations, and SGRQ (assessed for three sub-domains and the total score), to thoroughly assess the robustness of our results.

Individuals will be considered to have had some missing data for the two count variables if they have less than 47 weeks (48 weeks – 7day window) follow-up with the exception of those with planned truncated follow-up.

In the first approach, regardless of whether missingness is assumed to be random or non-random, we will perform the outlined statistical procedures. Additionally, we will provide descriptive characteristics of the missing group compared to the non-missing group, exploring potential similarities or dissimilarities between them. This comprehensive approach allows for a thorough examination of the impact of missing data on our study outcomes.

In the second approach, we are aware that throughout the trial, some participants may leave the study due to a high number of exacerbations or death before reaching their 48-week follow-up. This leads to missing data that is not at random, rendering

standard imputation methods inappropriate. Therefore, the data for key secondary outcomes for these participants will be analysed in the following way:

Pattern Mixture Model:

Robustness of the results will be assessed within the pattern mixture model. A pattern mixture model is a type of statistical model used to analyse data with missing values, especially when the missingness is not at random (MNAR).

This method is a 2-stage procedure where the 1st stage involves the use of multiple imputation to impute all missing values assuming data are “missing at random”.

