The 2nd stage involves changing the imputed values for those participants from the time that they leave the study due to a high number of exacerbations or death before reaching their 48-week follow-up.

For the 2nd stage, the following approach will be used:

- 1) Changing all imputed values for these participants to their last observation of the key secondary outcomes before they exit the study due to exacerbations or death. ^a
- 2) Adjusting all imputed values for participants who exit the study due to exacerbations or death to a constant value (i.e. the mean of the outcome variable in the control group). ^b

^a For the count variables, observed data will be carried forward by imputing the number expected in 48 weeks to be at the same rate as for the observed period rounded to the nearest whole number.

^b For the count variables, observed data will included for the time period observed with the number for the remaining time period being imputed at the rate observed in the control group (using all observed control data weighed for the time observed) rounded to the nearest whole number for that time period.

Note: For Stage 1, all missing data will be imputed using multiple imputation with chained equations in Stata 18 (or above). Stata’s “MI” command will be used to carry out this analysis and No data will be imputed past point of death.

Overall, 50 imputations will be generated for any missing data for the key secondary outcome and all stratification variables, treatment arm, and baseline value will be used to aid the multiple imputation procedure. Imputed results will be combined using Rubin’s rule which in Stata is the “mi estimate” command.

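### The SAP's missing-not-at-random sensitivity analysis replaces multiply imputed values with fixed ones; scaling a participant's own short-period event rate to 48 weeks gives wrong standard errors, and the rule on death conflicts with itself

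*SAP*

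**What the plan says.** SAP 6.5.3 covers three key secondary outcomes: number of readmissions, number of exacerbations, and SGRQ (total and three sub-domains). It accepts that people who leave because of many exacerbations, or who die, have data missing not at random, and it plans a two-stage pattern mixture model.

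- **Stage 1** makes 50 chained-equation imputations under missing at random. The listed predictors are that "all stratification variables, treatment arm, and baseline value will be used to aid the multiple imputation procedure".
- **Stage 2** acts on the leavers: "The 2nd stage involves changing the imputed values for those participants from the time that they leave the study".
  - Option 1: "Changing all imputed values for these participants to their last observation of the key secondary outcomes".
  - Option 2: "Adjusting all imputed values for participants who exit the study due to exacerbations or death to a constant value", namely the control-group mean.
- **Footnote a** (counts, option 1) means "imputing the number expected in 48 weeks to be at the same rate as for the observed period", rounded.
- **Footnote b** (counts, option 2) keeps the observed count and adds the control rate over the remaining time, rounded.
- **A note** that opens by referring to Stage 1 says "No data will be imputed past point of death".

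Results are pooled by Rubin's rules. The section gives no range of departures from missing at random, no tipping point, and no offset for the filled counts.

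**The concern.** Multiple imputation reflects uncertainty because each missing value differs between datasets. Stage 2 removes that variation for exactly the participants whose data the SAP considers most doubtful. For counts under footnote a there is a further problem. A rate seen over a few weeks, in people selected because they had events, is given the weight of 48 observed weeks.

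The SAP will use this analysis to judge whether the secondary results are robust. If its standard errors are wrong, it could confirm or overturn a result for reasons unrelated to the missing data. On death, two programmers could follow the same text and produce different datasets.

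**Working it through.** The SAP gives no numerical result for this analysis, so there is no figure to reproduce. It also gives no exit fraction; every fraction below is an assumption.

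**1. Pooling.** Rubin's total variance is T = W + (1 + 1/M)B, with M = 50. A value that is the same in all 50 datasets adds nothing to B. In W it counts as an observed value.

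**2. Footnote a, arithmetic.** Filled count = round(k × 48/w) for k events before exit at week w.

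| Exit week | 2 | 4 | 8 | 12 | 24 |
|---|---|---|---|---|---|
| k = 1 | 24 | 12 | 6 | 4 | 2 |
| k = 2 | 48 | 24 | 12 | 8 | 4 |

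With a 48-week offset the participant's rate is unchanged (24/48 = 1/2), but its weight is not. In a negative binomial model the weight is about μ/(1 + αμ), where μ is the expected count and α the dispersion. Assume 1.5 events per 48 weeks and α = 0.7:

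- 48 weeks: 1.5/(1 + 0.7 × 1.5) = 0.73
- 4 weeks: μ = 0.125, so 0.125/(1 + 0.7 × 0.125) = 0.115

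A participant seen for 4 weeks therefore gets about 0.73/0.115 = 6.4 times the weight that the data support. If the offset stayed at the observed time, 24 events would be set against 2 weeks, which is worse.

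**3. Footnote a, simulation.** Negative binomial counts, exit after two events, about 12% exiting, 48-week offset (all assumed), no treatment effect:

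- mean reported SE 0.168, actual SD of the estimate 0.206, ratio 0.168/0.206 = 0.82, so about 18% too small;
- null rejection 10.5% with equal exits and 18% with unequal exits, against about 6% from the observed data.

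The equal-exit figure agrees with the ratio: the effective critical value is 1.96 × 0.82 = 1.60, with a two-sided normal tail of about 11%.

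**4. Footnote b.** This rule does not inflate counts. At assumed control rates of 0.5 to 3 per year it adds 0 to 3 events. Rounding can erase the addition: 1 per year with 24 weeks left is 24/52 = 0.46, which becomes 0. In a separate count simulation with 10-20% exits, its SE was 3-7% below the observed-data SE.

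**5. SGRQ.** The mechanism shows most clearly with a single final visit (226 participants, SD 18, correlation parameter 0.6, random exit; SEs of the treatment effect):

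| Overwritten | 10% | 20% | 30% |
|---|---|---|---|
| Complete data | 2.11 | 2.13 | 2.12 |
| Imputation under missing at random | 2.23 | 2.38 | 2.56 |
| Same, with fixed +8 shift | 2.26 | 2.42 | 2.60 |
| Control mean | 2.03 | 1.95 | 1.84 |
| Last observation | 2.07 | 2.04 | 1.99 |

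Both fixed rules give SEs below those of a trial with nothing missing. The shift keeps the draws and does not.

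The SAP's model (6.5.1.2) has repeated measures, and Stage 2 acts only from the time of exit, so the effect is smaller. In a random-intercept simulation with 20-30% random exits, the control-mean SE was 6-9% below the observed-data SE overall and 11-17% below at the final visit. The final visit matters because 6.5.1.2 also plans treatment effects by visit. Last observation carried forward gave SEs 2-4% larger overall, but equal to the full-data SE at the final visit.

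**6. Death.** Stage 2 names death as an exit reason whose imputed values are changed, and footnote a runs to 48 weeks with no cap. The note bars imputation past death. If the note governs, Stage 2 has nothing to change after a death. If Stage 2 governs, values follow death. SAP 6.5.2 caps time at death for the per-protocol counts; 6.5.3 has no matching statement for either footnote.

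**The case against.** Several points on the other side stand.

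- **Death.** A reader might infer that the plan imputes outcomes for the dead. The note says the opposite. The documents support only an unresolved conflict.
- **Extreme counts.** A reader might infer that single early events routinely become dozens. One event reaches 24 only with exit by about week 2, and footnote b does not inflate. Protocol 7.8 asks those who stop treatment for continued admission and death data, and 7.11 traces lost participants through hospital records. This should limit early loss of readmission data. It protects SGRQ less, and moderate exacerbations, which by definition are not hospitalised.
- **Interval width.** A reader might infer that every interval is much too narrow. Under the repeated-measures model, last observation carried forward is not narrower overall. The control-mean SE at 5% and 10% exits was only 1% and 3% below the observed-data SE. With equal exits, null rejection for SGRQ was not inflated. Unequal exits were not tested under that model.
- **Robustness.** A reader might say that the analysis barely tests robustness. That is a judgement. Giving mepolizumab leavers the control mean pulls the estimate towards no effect, and reference-based draws centre on the same place. A missing-at-random analysis and a comparison of missing with non-missing participants are also planned.
- **Stage 1 predictors.** A reader might infer that Stage 1 ignores events and time already observed. The SAP lists variables that aid the imputation without calling the list complete, so this rests on silence.

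None of this rescues footnote a. Its SE is wrong for its own estimator, even with equal exits.

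**Conclusion.** The concern holds in a limited form. Stage 2 replaces draws with fixed values, and pooling treats these as data.

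- **Footnote a** is the clear error: SE about 18% too small and null rejection 10-18%, with about 12% exits after two events and a 48-week offset, both assumed. The size depends on how early people leave.
- **Control mean for SGRQ** claims more precision than the data hold: 6-9% overall and 11-17% at the final visit at 20-30% exits, and less at lower fractions. **Last observation** reports the final visit as if nothing were missing.
- **Death** is a conflict within 6.5.3 that must be reconciled.

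The scope is a sensitivity analysis of key secondary outcomes. The primary Cox analysis and the sample size do not depend on it.

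**What to change.** Amend SAP 6.5.3 before database lock:

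1. **SGRQ.** Keep the Stage 1 draws and apply a pre-specified range of delta shifts, or use reference-based draws. Retain residual variation and pool by Rubin's rules.
2. **Counts.** Keep observed events. Draw only the unobserved remainder from the negative binomial model, conditional on events and time observed, at the control rate or at the own-arm rate times a stated range of multipliers. Drop the scaling of each participant's own rate and the rounding. State the offset.
3. **Death.** State that Stage 2, both footnotes and the count offset stop at death.

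The cost is SAP wording and modest programming, with multiple imputation already planned in Stata. Sensitivity intervals will be somewhat wider.

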6.6 Subgroup Analyses

Subgroup analyses of the primary outcome will be carried out on the stratification factors. These are baseline eMRC dyspnoea stable state score (≤ 3 , > 3) and past hospitalisation in the previous 12 months (0 , ≥ 1). A stratified Cox model will be fitted to allow the form of the underlying hazard function to vary across the levels of stratification variables.

Three subgroup analyses of the primary outcome will be carried out based on

- 1) baseline dyspnoea stable state score dichotomised by ≤ 3 and > 3 and
- 2) past hospitalisation in the previous 12 months dichotomised by 0 and ≥ 1
- 3) WHO clinical progression score at baseline (4, 5, 6).

The primary outcome of time to hospital re-admission or death (all cause) will be summarised by each subgroup (low versus high) and analysed as described in section 5.5.1. In each subgroup model, an indicator variable to specify the stratification group (low or high) will be included and an interaction term between stratification variable and treatment group will assess the difference in treatment efficacy between low and high stratification variable groups.

6.7 Adjusted Analysis

Modelling of the primary and all secondary outcomes will be adjusted for the baseline eMRC dyspnoea stable state score (≤ 3 , > 3) and past hospitalisation in the previous 12 months (0 , ≥ 1), used as a stratification factor at randomisation.

Adjustment for stratification variables can only take place where the statistical model allows for specification of such variables.

6.8 Changes to the Planned Analysis

None.

7 Safety and Adverse events

All safety data will be presented according to the Safety population.

All adverse events will be listed including characteristics such as seriousness, duration, relatedness, severity, action taken and outcome.

Adverse events' frequencies by seriousness, relatedness and severity will be summarised by treatment group and overall.

Adverse events frequencies will also be presented by treatment arm for each MedDRA Coding system organ class observed.

Graphical illustrations of frequencies by arm in total and by system organ class will be presented.

Furthermore, AE and SAE event rates will be reported as incidence rates per person years and calculated as (total number of events / sum of all follow-up times) *52 where;

- Total number of events is a count of all AE/SAEs observed.

- Follow-up time is calculated per participant from time of first dose until the last trial assessment is recorded.

8 References

Dodd, J. W., Hogg, L., Nolan, J., Jefford, H., Grant, A., Lord, V., ... Hopkinson, N. S. (2011). The COPD Assessment Test (CAT) - Response To Pulmonary Rehabilitation. A Multicentre, Prospective Study. *Thorax*, 66, 425–429.

Muller, J. P., Gonçalves, P. A., Fontoura, F. F., Mattiello, R., & Florian, J. (2013). Applicability of the London Chest Activity of Daily Living scale in patients on the waiting list for lung transplantation. *Jornal brasileiro de pneumologia : publicacao oficial da Sociedade Brasileira de Pneumologia e Tisiologia*, 39(1), 92–97.

9.1 Appendix 1: Templates for Tables, Listings and Figures

Table1: Disposition of Patients by treatment arm

	Control, n (%)	Mepolizumab, n (%)	Total, n (%)
Randomised patients			
Completed trial follow-up (End of trial assessment)			
Discontinued due to			
Lost to follow-up			
Withdrawn			
Deaths			
Remained on treatment for intended follow-up period			
Discontinued treatment early			
Reasons:			
Participant decision			
Adverse Event			
Unable to Tolerate Drug			
Participant non-compliance			
Lost to Follow up			
Investigator decision			
Participant Ineligible			
Withdrawn due to Medical Reasons			
Death			
Number of doses received			
1			
2			
3			
4			
5			
6			
7			
8			
9			
10			
11			
12			

Figure 1: A Swimmer plot of participants' discontinuation from the trial with reasons

Table 1: Case Report Form (CRF) return

CRF	Placebo Returned/Expected (%)	Mepolizumab
Visit 1 (Week 0)	Follow-up due	
	Follow-up completed	
Visit 2 (Week 4)	Follow-up due ^a	
	Follow-up completed	
Visit 3 (Week 8)	Follow-up due ^a	
	Follow-up completed	
Visit 4 (Week 12)	Follow-up due ^a	
	Follow-up completed	
Visit 5 (Week 16)	Follow-up due ^a	
	Follow-up completed	
Visit 6 (Week 20)	Follow-up due ^a	
	Follow-up completed	
Visit 7 (Week 24)	Follow-up due ^a	
	Follow-up completed	
Visit 8 (Week 28)	Follow-up due ^a	
	Follow-up completed	
Visit 9 (Week 32)	Follow-up due ^a	
	Follow-up completed	
Visit 10 (Week 36)	Follow-up due ^a	
	Follow-up completed	
Visit 11 (Week 40)	Follow-up due ^a	
	Follow-up completed	
Visit 12 (Week 44)	Follow-up due ^a	
	Follow-up completed	
Visit 13 (Week 48)	Follow-up due ^a	
	Follow-up completed	

^a Will be defined as participants who have passed the visit window stated in the Protocol.

Table 2: Demographic and Baseline Clinical Characteristics

Characteristics	Descriptive	Placebo (n=)	Mepolizumab (n=)	Total (n=)
Age	N			
	Mean [SD]			
	Median [IQR]			
	Min, Max			
Gender	Male			
	Female			

Ethnicity	White
	Asian or Asian British
Smoking status	Current Smoker
	Ex-Smoker
BMI	N
	Mean [SD]
	Median [IQR]
	Min, Max
Number of cigarettes per day	N
	Mean [SD]
	Median [IQR]
	Min, Max
Number of years smoked	N
	Mean [SD]
	Median [IQR]
	Min, Max
Number of emergency admissions (all cause) in previous 12 months	N
	Mean [SD]
	Median [IQR]
	Min, Max
Number of courses of steroids without antibiotics for your chest (COPD exacerbations) in previous 12 months	N
	Mean [SD]
	Median [IQR]
	Min, Max
Number of courses of antibiotics without steroids for your chest (COPD exacerbations) in previous 12 months	N
	Mean [SD]
	Median [IQR]
	Min, Max
Number of courses of both antibiotics and steroids for your chest (COPD exacerbations) in previous 12 months	N
	Mean [SD]
	Median [IQR]
	Min, Max
Systolic (mmHg)	N
	Mean [SD]
Pre-Dose	Median [IQR]
	Min, Max
Diastolic (mmHg)	N
	Mean [SD]
Pre-Dose	Median [IQR]
	Min, Max
Heart rate (bpm)	N
	Mean [SD]
Pre-Dose	Median [IQR]
	Min, Max
Temperature (°C)	N
	Mean [SD]

Pre-Dose	Median [IQR]
	Min, Max
SpO ₂ (%)	N
	Mean [SD]
Pre-Dose	Median [IQR]
	Min, Max
Respiratory rate (per min)	N
	Mean [SD]
Pre-Dose	Median [IQR]
	Min, Max
Systolic (mmHg)	N
	Mean [SD]
Post-Dose	Median [IQR]
	Min, Max
Diastolic (mmHg)	N
	Mean [SD]
Post-Dose	Median [IQR]
	Min, Max
Heart rate (bpm)	N
	Mean [SD]
Post-Dose	Median [IQR]
	Min, Max
Temperature (°C)	N
	Mean [SD]
Post-Dose	Median [IQR]
	Min, Max
SpO ₂ (%)	N
	Mean [SD]
Post-Dose	Median [IQR]
	Min, Max
Respiratory rate (per min)	N
	Mean [SD]
Post-Dose	Median [IQR]
	Min, Max
eMRC dyspnoea score (stable state)	
2: Breathless when hurrying on the level or walking up a slight hill
 
3: Walks slower than peers or stops when walking on the flat at own pace
 
4: Stops after walking 100m, or for a few minutes, on the level
 
5A: Too breathless to leave the house & independent in washing and/or dressing

	5B: Too breathless to leave the house & dependent in washing and dressing
	Missing*
WHO: Highest level of intervention during baseline admission	No oxygen therapy
	Oxygen by mask or nasal prongs
	Oxygen by NIV or high flow
Time to discharge from index admission (days)	N
	Mean [SD]
	Median [IQR]
	Min, Max
*FEV1, litre	N
	Mean [SD]
	Median [IQR]
	Min, Max
*FEV1, %	N
	Mean [SD]
	Median [IQR]
	Min, Max
*FVC, litre	N
	Mean [SD]
	Median [IQR]
	Min, Max
*FVC, %	N
	Mean [SD]
	Median [IQR]
	Min, Max
*FEV1/FVC ratio, %	N
	Mean [SD]
	Median [IQR]
	Min, Max

Abbreviations: SD= Standard deviation; IQR= Inter-quartile range, Min=Minimum; Max=Maximum; N= number of observations

Data are n (%), mean (SD), or median (IQR), unless otherwise stated.

Figure 2: Proportion of patients in each dose

Figure 3: Number of doses per patient

Figure 4: Kaplan-Meier survival curves of the primary outcome by randomised group

Table 4: Primary Analysis of Primary Outcome: the time from randomisation to next hospital readmission or death (all cause)

	KM survival estimates at 48 weeks		Cox PH Model ^a	
	Placebo (n=)	Mepolizumab (n=)	HR (95% CI)	p-value
Intention to treat analysis				

a The Cox proportional hazard model will be used for the primary outcome of the time to re-hospitalisation or death (any cause) as the dependent variable. The treatment group served as an explanatory factor, while baseline MRC dyspnoea score (≤ 3 , >3) and past hospitalisation in the previous 12 months (0, ≥ 1) will be included as stratification factors.

Table 5: Protocol deviations by treatment arm and overall

	Placebo	Mepolizumab
Randomised participants		
Randomised participants with Protocol Deviations		
Participants with:		
No Protocol Deviations		
1 Protocol Deviation		
2 Protocol Deviations		
3 Protocol Deviations		
4 Protocol Deviations		
5 Protocol Deviations		
≥ 6 Protocol Deviations		

Table 5: Number of Major and Minor Protocol Deviations

	Placebo	Mepolizumab
Number of Major Protocol Deviations		
Description		
Participant ineligible for entry into Trial		
Number of Minor Protocol Deviations		
Description		
Participant ineligible for entry into Trial		
Non-compliance with treatment allocation		
Visit/assessment not performed as per Protocol		
Other		

Table 6: Number of participants with Adverse Events

	Placebo	Mepolizumab
Randomised participants		
Randomised participants with Adverse Events		
Participants with:		
No Adverse Events		
1 Adverse Event		
2 Adverse Events		
3 Adverse Events		
4 Adverse Events		
≥ 5 Adverse Events		

Figure 7: Frequency of AE term by treatment arm

Table 7: Prevalence of AEs and SAEs by relatedness and severity

	Placebo	Mepolizumab
Number of Adverse Events		
Severity		
Mild		
Moderate		
Severe		
Fatal		
Missing		
Outcome		
Resolved		
Resolved with Sequelae		
Continuing		
Fatal*		
Unknown		
Missing		
Treatment		
None		
Concomitant Medication		
Non-drug therapy		
Concomitant Medication and Non-drug therapy		
Missing		
Action taken for Adverse Event		
None		
Study interrupted		
Study discontinued		
Missing		

	Placebo	Mepolizumab
Relatedness		
	Not related	
	Unlikely	
	Possible	
	Probable	
	Definite	
	Missing	
Serious Adverse Event?		
	Yes	
	No	
	Missing	
Expectedness		
	Yes	
	No	
	Missing	

9.2 *Appendix 2: Line listing of the adverse events*

Preferred AE term	AE system	Seriousness	Start date	End date	Relatedness	Severity	Outcome	Treatment arm
